6.2 GEN-003/Placebo Dosing Period

6.2.1 Maintenance Dose (Day 1) – Clinic Visit

The visit will take approximately 2.5 hours, including observation for 1 hour after vaccination.

Dosing must be delayed if the following criterion is met:

- Febrile illness (temperature $\geq 38.0^{\circ}\text{C}$) or other acute illness within the past 48 hours

The subject may be dosed once the criterion has been resolved and the criterion is no longer met.

The following procedures will be performed for screening:

- Written informed consent
- Medical history, including medication and vaccine history
- Weight
- Urine pregnancy test for all women

Eligibility for study enrollment will be checked. If a subject is excluded because of exclusion criteria 1 (important protocol deviation in Study GEN-003-003), 6 (immunocompromise), 7 (AEI), or 8 (autoimmune disease), then the details of the excluding deviation, diagnosis, or medication will be entered in the eCRF.

Upon determination that a subject meets all eligibility criteria, the following blood samples will be collected:

- Serum for future research
- At selected investigational sites: whole blood for PBMC isolation for future research

The subject will then be **randomized** to treatment assignment (as described in Section 5.2) and GEN-003/placebo administered.

The subject will remain at the investigational site for observation for at least 1 hour, and the following procedures will be performed 1 hour after GEN-003/placebo administration:

- Assessment of local reactions, systemic events, and AEs

Before discharge from the clinic, the subject will be given a Diary Card and instructed to record temperature, local reactions, and systemic events (at the same time each day). The subject will also be instructed that, if any event is ongoing after Day 8, to follow the event until resolution and report the stop date. The subject will be instructed to bring the Diary Card back to the clinic at the next visit.

Before discharge from the clinic, the subject will be given a pad of EQ-5D-5L questionnaires and instructed to complete 1 questionnaire each day of the first genital herpes recurrence.

If needed, the subject will be provided with an electronic device for use of the daily electronic reporting tool. The subject will be instructed in use of the daily electronic reporting tool. The subject will be asked to log into the system to ensure access before leaving the site.

6.2.2 Day 8 (\pm 3 Days) – Clinic Visit

The following procedures will be performed:

- Review of daily electronic reporting tool data
- Collection of completed EQ-5D-5L questionnaires, if completed
- Review of Diary Card
- Sample collection:
 - Serum for future research
 - At selected investigational sites: whole blood for PBMC isolation for future research
- Assessment of AEs (including SAEs, AESIs, and MAAEs)
- Assessment of concomitant medications and vaccines

The subject will be reminded to continue use of the daily electronic reporting tool.

6.2.3 Day 29/Month 1 (\pm 3 Days) – Clinic Visit

The following procedures will be performed:

- Review of daily electronic reporting tool data
- Collection of completed EQ-5D-5L questionnaires, if completed
- Sample collection:
 - Serum for pregnancy test for all women (unless surgically sterilized)
 - Serum for future research
 - At selected investigational sites: whole blood for PBMC isolation for future research
- Assessment of AEs (including SAEs, AESIs, and MAAEs)
- Assessment of concomitant medications and vaccines

The subject will be reminded to continue use of the daily electronic reporting tool.

6.3 Follow-up Period

6.3.1 Follow-up Telephone Calls

Follow-up telephone calls will be made at each of the following time points:

- Month 2 (Day 57 ± 7 days)
- Month 4 (Day 113 ± 7 days)
- Month 8 (Day 225 ± 14 days)
- Month 10 (Day 281 ± 14 days)

The following procedures will be performed:

- Review of daily reporting tool data (Month 4 only)
- Assessment of SAEs, AESIs, and MAAEs
- Assessment of antiviral medication through Month 6

The subject will be reminded to continue use of the daily electronic reporting tool.

6.3.2 *Month 3 (Day 85 ± 7 days) and Month 6 (Day Day 169 ± 14 days) – Clinic Visits*

The following procedures will be performed:

- Review of daily electronic reporting tool data
- Collection of completed EQ-5D-5L questionnaires, if completed
- Assessment of SAEs, AESIs, and MAAEs
- Assessment of antiviral medication

6.3.3 *Month 9 (Day 253 ± 14 days) and Month 12 (Day 337 ± 14 days) – Clinic Visits*

The following procedures will be performed:

- Assessment of SAEs, AESIs, and MAAEs

7 ADVERSE EVENTS

AEs will be reported in a manner consistent with the FDA Guidance for Industry and Investigators, "Safety Reporting Requirements for IND and BA/BE Studies," December 2012 (<http://www.fda.gov/downloads/Drugs/GuidanceComplianceRegulatoryInformation/Guidances/UCM227351.pdf>).

7.1 Reporting Responsibilities

All AEs (including SAEs, AESIs, and MAAEs) will be recorded from the maintenance dose to Day 29/Month 1. After Day 29/Month 1 to the end of study, only SAEs, AESIs, and MAAEs will be recorded. It is the responsibility of the Investigator or Subinvestigator(s) to perform periodic assessment of AEs. Data describing AEs will be entered in the subject's medical record and eCRF, and as appropriate, an SAE/AESI report form. SAEs and AESIs will be reported to the Sponsor as described in Section 7.6.

7.2 Definitions

7.2.1 Adverse Event

An AE is any untoward medical occurrence in a patient or clinical investigation subject administered a pharmaceutical product and which does not necessarily have a causal relationship with this treatment. An AE can therefore be any unfavorable and unintended sign (including an abnormal laboratory finding), symptom, or disease temporally associated with the use of an IP, whether or not related to the IP.

7.2.2 Medically Attended Adverse Events

A MAAE is an AE resulting in hospitalization, emergency room visit, or visit to or from medical personnel (other than routine health care visits). If a MAAE is "hospitalization" it should be reported as an SAE as described in Section 7.6 below.

7.2.3 Adverse Event of Special Interest

Refer to [Appendix 4](#) for the list of AESIs.

7.2.4 Serious Adverse Event

An AE or suspected adverse reaction is considered serious (an SAE) if, in the view of either the Investigator or Sponsor, it results in any of the following outcomes:

- Death
- Life-threatening (An AE is considered life-threatening if, in the view of either the Investigator or Sponsor, its occurrence places the patient or subject at immediate risk of death. It does not include an AE that, had it occurred in a more severe form, might have caused death.)
- Inpatient hospitalization or prolongation of existing hospitalization

- A persistent or significant incapacity or substantial disruption of the ability to conduct normal life functions
- A congenital anomaly/birth defect

Important medical events that may not result in death, be life-threatening, or require hospitalization may be considered serious when, based upon appropriate medical judgment, they may jeopardize the patient or subject and may require medical or surgical intervention to prevent one of the outcomes listed in this definition. Examples of such medical events include allergic bronchospasm requiring intensive treatment in an emergency room or at home, blood dyscrasias or convulsions that do not result in inpatient hospitalization, or the development of drug dependency or drug abuse.

If it is not certain that an event meets the above definitions of an SAE, contact the Medical Monitor to discuss.

7.2.5 Relatedness (Causality)

Causality (relationship to GEN-003/placebo) assessment is required for all AEs that occur during clinical studies. The following terms will be used during this study:

- **Likely** - Reasons to consider an AE likely related to treatment may include, but are not limited, to the following:
 - Timing of the event relative to the administration of the IP
 - Location of the AE relative to the site of IP administration
 - Likelihood based on experience with similar products
 - A biologically plausible explanation based on the mechanism of action or mode of delivery of the treatment
 - The AE is repeated on subsequent treatments.
 - No other explanation is likely.
- **Unlikely** - An AE with no temporal association with the IP but rather related to other etiologies such as concomitant medications or conditions or subject's known clinical state

7.2.6 Severity

Severity for all AEs, including laboratory abnormalities, will be reported in accordance with Toxicity Grading Scale for Healthy Adult and Adolescent Volunteers Enrolled in Preventive Vaccine Clinical Trials ([Appendix 2](#)).

If an appropriate listing is not present in this table for an AE, the AE will be graded as follows:

- **Grade 1 (Mild)** - No interference with daily activity
- **Grade 2 (Moderate)** - Some interference with daily activity but medical intervention not required (e.g., doctor visit and/or prescription medicine); over-the-counter medicine permitted

- **Grade 3 (Severe)** - Prevents daily activity and requires medical intervention (e.g., doctor visit and/or prescription medicine)
- **Grade 4 (Potentially Life-threatening)** - Emergency room visit or hospitalization

7.3 Clinical Laboratory Abnormalities

Any laboratory abnormality deemed clinically significant by the Investigator should be recorded as an AE. A clinically significant abnormality is a confirmed abnormality (by repeat test) that is changed sufficiently from Screening/baseline so that in the judgment of the Investigator a change in management is warranted. This alteration may include monitoring the laboratory test further, initiating other diagnostic tests or procedures, changing ongoing treatment, or administering new treatment.

Whenever possible, the underlying medical diagnosis (e.g., anemia) should be recorded as the AE term. Repeated additional tests and/or other evaluations required to establish the significance and etiology of an abnormal result should be obtained when clinically indicated.

7.4 Physical Exam Abnormalities

Any physical exam abnormality deemed clinically significant by the Investigator at Day 1 should be reported as medical history. Any new physical exam abnormality deemed clinically significant by the Investigator during the study should be reported as an AE.

7.5 Pregnancy

The ICF will include information regarding reporting of pregnancy to the Sponsor and collection of information through the end of pregnancy in both subjects and female partners of male subjects. If a female partner becomes pregnant, the Investigator will request consent from the partner to collect this information.

All remaining safety assessments should be performed for a subject who becomes pregnant. All pregnancies that occur during the study—including pregnancies in female partners of male subjects must be reported to the Sponsor on the Pregnancy eCRF and followed to conclusion. The outcome of each pregnancy must also be reported on the Pregnancy eCRF. Pregnancy alone is not an AE, nor is an induced elective abortion to terminate a pregnancy without medical reason. However, an induced therapeutic abortion to terminate a pregnancy due to complications or medical reasons must be reported as an SAE. The underlying medical diagnosis for this procedure should be reported as the SAE term. A spontaneous abortion is always considered an SAE.

7.6 Reporting of Serious Adverse Events and Adverse Events of Special Interest

SAEs and AESIs must be reported to the Sponsor or designee within 1 business day of becoming aware of the event by entering the data on the AE eCRF. If at the time the Investigator submits an initial SAE/AESI report the event has not resolved, the Investigator must provide a follow-up as soon as it resolves (or upon receipt of significant information if the event is still ongoing). All

SAEs/AESIs must be followed until resolution/stabilization or until a time that is mutually agreed upon between the Medical Monitor and the Investigator. Upon checking serious or AESI on the AE eCRF, a notification will be sent to the Medical Monitor and/or designee. Relevant eCRFs (including Medical History, Concomitant Medications, and Adverse Events) must also be completed to provide supporting documentation for the SAE/AESI. If there are additional documents that support the SAE/AESI (e.g., clinic or hospital records or procedure reports), they should be uploaded to the AE eCRF.

After review of the initial SAE/AESI information, the Medical Monitor may request additional documentation.

The Sponsor is responsible for notifying the relevant Regulatory Authorities of certain events. It is the Investigator's responsibility to notify the IRB/EC of all SAEs that occur at his or her site. Investigators will also be notified of all unexpected, serious, IP-related events that occur during the clinical trial. Each site is responsible for notifying its IRB/EC of these additional SAEs.

7.7 Follow-Up of Adverse Events

A subject who experiences any AE, whether serious or not serious, will be monitored at appropriate intervals and receive appropriate treatment and medical supervision as clinically indicated. All AEs must be followed until resolution/stabilization or until a time that is mutually agreed upon between the Medical Monitor and the Investigator. Clinically significant laboratory abnormalities should be confirmed within 48 hours or as soon as clinically indicated and then followed weekly until resolution.

8 SUBJECT AND STUDY DISCONTINUATION

Subjects withdrawn from the study will not be replaced, regardless of the reason for withdrawal.

8.1 Screening Failures

Subjects who sign and date the informed consent form (ICF) but who fail to meet the inclusion and exclusion criteria (Section 4) are defined as screen failures. A screening log, which documents the subject's initials and reason(s) for screen failure, will be maintained by the Investigator for all screen failures. A copy of the log should be retained in the Investigator's study files.

If a subject fails screening because of Exclusion Criteria 1 (important protocol deviation in Study GEN-003-003), 6 (immunocompromise), 7 (AESI), or 8 (other autoimmune disease), then the details of the excluding deviation, diagnosis, or medication will be entered in the eCRF.

8.2 Premature Discontinuation from Study

A subject may be prematurely discontinued from the study for any of the following reasons:

- Withdrawal of consent
- Loss to follow-up
- Death
- Noncompliance or unwillingness to comply with the procedures required by the protocol
- Investigator discretion
- Sponsor request
- Site termination
- Study termination

8.3 Procedures for Premature Discontinuation from Study

If a subject prematurely discontinues the study prior to Day 29/Month 1, then the procedures listed for Day 29/Month 1 (Section 6.2.3) should be performed.

If a subject prematurely discontinues the study after Day 29/Month 1, then the procedures listed for Month 12 (Section 6.3.4) should be performed.

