Section 6.3.3 – Months 9 and 12	The following procedures will be performed: 
 • Assessment of SAEs, AESIs, and MAAEs 	Combined procedures for Months 9 and 12 (changed from 6 and 12) to reflect new data collection periods and elimination of blood sampling
Original Section 6.3.3 – Months 5 and 11	Deleted entire section	No longer required
Original Section 6.3.4 – Months 6 and 12	Deleted entire section and replaced with new section 6.3.3	See above
Section 10.4 – Subject Disposition, ¶3	Analysis populations will be summarized in a tabular format.	Data will be presented in listings only
Section 10.7 – Primary Efficacy Endpoint	Genital herpes lesion rates (the proportion of days with genital lesions present) in the 12 6-month period after the maintenance dose will be compared between treatment groups using the Wilcoxon rank sum test.	To reflect analysis of new observation period
Section 10.8.1 – Frequency of Genital Herpes Recurrences, sentence 1	The frequency of genital herpes recurrences in the 12 6-month period after the maintenance dose will be calculated as the number of recurrences reported and summarized by mean, SD, median, and range.	Reflect analysis of new observation period
Section 10.8.2 – Proportion of Subjects Recurrence-Free	The proportion of subjects in each treatment group who are genital herpes recurrence-free at 12 6 months after the maintenance dose will be tabulated and compared using a chi-square test for homogeneity of proportions.	Reflect analysis of new observation period

Section	Change	Rationale
Section 10.8.3 – Time to First Genital Herpes Recurrence	Time to first recurrence in the 12 6-month period after the maintenance dose will be tabulated and graphed using the Kaplan-Meier method. The log-rank test will be used to compare the time to first recurrence survival curves between the GEN 003 and placebo groups. Survival analysis with Cox model will be used to compare the time to next genital herpes recurrence.	Reflect analysis of new observation period; time to “next” recurrence will not be analyzed
Section 10.8.4 – Duration of Genital Herpes Recurrences, sentence 1	Duration of genital herpes recurrences over the 12 6-month period after the maintenance dose will be calculated and summarized by mean, SD, median, and range.	Reflect analysis of new observation period
Section 10.8.5 – Anogenital Shedding Rate	Deleted entire section	Genital swabbing has been eliminated from the protocol

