## **11 EFFICACY ANALYSIS**

### **11.1 Genital Herpes Lesion Rate**

Lesion rate (days) is defined as number of days with lesions divided by the time period of follow-up for lesions (in days). The days with lesions will be collected continuously throughout the study via an electronic lesion diary, and lesion rates will be calculated for the following periods: Baseline and Day 1 to 183 (post-dosing). For the purposes of determining days with lesions, a diary entry of missing will be treated the same as a diary entry of “no,” except in the following case: if 1 or 2 consecutive instances of missing is flanked by “yes” values on both sides, those missing values will be treated as a “yes” value.

Lesion rate will be analyzed with descriptive summary tables for overall and individual lesion rates calculated for the periods noted above. Individual subject lesion rates will be compared for the active treatment group vs. placebo using the Wilcoxon rank sum test.

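### Section 8.3 points leavers after Day 29 to a section that no longer exists and to a safety-only visit list, so antiviral use since the last contact is not asked about when a subject leaves before Month 6

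*Protocol*

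**What the plan says.** Protocol Section 8.3 has two rules. For a subject who discontinues before Day 29, "then the procedures listed for Day 29/Month 1 (Section 6.2.3) should be performed". For a subject who discontinues after Day 29, "then the procedures listed for Month 12 (Section 6.3.4) should be performed".

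Section 6.2.3 exists, and its list includes diary review, EQ-5D-5L collection and concomitant medications. Section 6.3.4 does not exist. Month 12 is now covered by Section 6.3.3, headed "Month 9 (Day 253 ± 14 days) and Month 12 (Day 337 ± 14 days) – Clinic Visits", and that section lists one procedure: "Assessment of SAEs, AESIs, and MAAEs". The Month 12 column of Appendix 1 agrees.

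The assessments that serve the six-month efficacy period are in Section 6.3.2 (Months 3 and 6): diary review, "Collection of completed EQ-5D-5L questionnaires, if completed", safety, and antiviral medication. The telephone calls in Section 6.3.1 add "Assessment of antiviral medication through Month 6". Section 5.5 requires antiviral use to be recorded from Day 1 to Month 6.

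The amendment log in Appendix 6 explains how the reference was left behind. Of the former Section 6.3.4 it records: "Deleted entire section and replaced with new section 6.3.3". The error is in the current text of 8.3, which still cites the deleted section.

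**The concern.** A site cannot carry out the instruction as cited. If it takes the obvious substitute, Section 6.3.3, it performs a safety check and nothing else. A subject leaving on Day 28 is therefore asked about medications and hands in questionnaires. One leaving on Day 30, with about five months of the efficacy period still to run, has neither step prescribed.

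Antiviral use is what is at stake, because no other route clearly captures it. Section 11.8 says that subjects record it in the daily tool, but the tool description in Section 6.1 and the diary in Appendix 5 contain no antiviral item. On those two descriptions, antiviral use is known only if the site asks. Two outputs depend on it:

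- **Per-protocol membership.** Suppressive antiviral therapy is an important protocol deviation (Protocol 11.7), and such a deviation removes a subject from the per-protocol set (Protocol 10.3, SAP 4.3).
- **The antiviral summaries.** SAP 11.6 summarises use over six months. The shell for Table 14.2.8.1 has rows for Yes and No only, so a leaver who was not asked may be counted as No. Table 14.2.5.1, by contrast, gives leavers an Unknown row.

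**Working it through.** The plan gives no figure to reproduce. The check compares the procedure lists and then takes differences between scheduled contact days.

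**1. What is prescribed at exit**

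| Assessment | Leaves before Day 29 (6.2.3) | Leaves after Day 29, under 8.3 (Month 12 list, 6.3.3) | Month 3/6 list (6.3.2) |
|---|---|---|---|
| Diary review | yes | no | yes |
| EQ-5D-5L collection | yes | no | yes |
| Antiviral or concomitant medication | yes | no | yes |
| Safety assessment | yes | yes | yes |

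The affected span runs from Day 29 to the nominal Month 6 visit: 169 − 29 = 140 days.

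**2. Antiviral use that can go unasked**

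Antiviral use is assessed at Day 29 (as concomitant medication), the Month 2 call (Day 57), the Month 3 visit (Day 85), the Month 4 call (Day 113) and the Month 6 visit (Day 169). The longest stretch since the last contact is the gap between neighbouring contacts:

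- 57 − 29 = 28, 85 − 57 = 28 and 113 − 85 = 28 days before Month 4.
- 169 − 113 = 56 days between Month 4 and Month 6.
- With the visit windows at their extremes, the last gap is (169 + 14) − (113 − 7) = 77 days.

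Against the SAP's window of Days 1 to 183, 56/183 = 31% and 28/183 = 15%.

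**3. EQ-5D paper forms**

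Forms are collected at Day 29, Month 3 and Month 6. The gaps are 85 − 29 = 56 and 169 − 85 = 84 days.

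**4. Lesion diary**

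Entries are electronic and already held when the subject leaves. Section 6.1 has site staff review them every week, so about 7 days of review are outstanding at most.

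**5. Which leavers can stay in the per-protocol set**

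The set also requires diary data on at least 80% of days, and neither document fixes the denominator for a leaver. If it stops at the discontinuation date, as percent compliance does in Table 14.2.1, any leaver can qualify. If it is all 183 days, 0.80 × 183 = 146.4, so only a subject leaving on Day 147 or later can. Those subjects fall in the 56-day gap after Month 4.

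**The case against.** The strongest reply is that this is a stale cross-reference with little behind it. Most of the supporting facts are right:

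- Antiviral use is assessed at every contact up to Month 4, so only the last stretch is exposed.
- Section 5.5 requires recording whatever 8.3 says, and a careful site may ask anyway.
- Suppressive use affects per-protocol membership, not the modified intent-to-treat set, and every efficacy table marked for the interim analysis uses the latter.
- The Month 6 window opens on Day 155, so a later leaver might be given the Month 6 assessments. A subject leaving before it opens has at most 154 − 113 = 41 unasked days on nominal timing, 22% of 183.
- Subjects who are lost to follow-up or die have no exit assessment under any wording.

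These points limit the size but do not remove the defect. Section 8.3 is the operative instruction for leavers, it does not mention using the Month 6 visit, and its list omits what 5.5 requires.

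A reader might go further and infer that the primary endpoint is damaged, since SAP 11.1 says "For the purposes of determining days with lesions, a diary entry of missing will be treated the same as a diary entry of" no, apart from one or two blank days lying between lesion days. The documents do not support that step. Lesion days come from the daily tool, which has reminders and weekly site review. The diary asks about the last 24 hours, and neither document describes filling earlier blanks at a visit, so a final review would not clearly change them and could not supply days after departure. The scoring of blanks is a separate matter. Time to first recurrence is censored at the last documented recurrence-free record (SAP 5.5.5), which needs no exit visit.

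**Conclusion.** Section 8.3 is wrong as written: its reference is dead, and the list it evidently intends prescribes no antiviral assessment, diary review or EQ-5D collection for a subject leaving between Day 29 and Month 6. The material loss is antiviral use since the last contact, with the nominal 56 days after Month 4 as the largest gap. The effect reaches per-protocol membership and the antiviral tables. EQ-5D is not an endpoint and appears only in Listing 16.2.6.2.

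The size is per subject. The documents give no expected number of leavers, so no effect on any estimate can be calculated. The conclusion assumes that sites do only what 8.3 and 6.3.3 list, and that Section 6.1 and Appendix 5, rather than 11.8, describe the tool correctly. If the tool does record antiviral use daily, most of the loss disappears.

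**What to change.** Rewrite the second rule in Section 8.3 so that discontinuation after Day 29 and before Month 6 uses the Month 6 data-collection list (6.3.2), and discontinuation after Month 6 uses the Month 12 list (6.3.3). Reconcile Section 11.8 with 6.1 and Appendix 5 so that the protocol states one route for recording antiviral use. As an optional addition, give Tables 14.2.8.1 and 14.2.8.2 an Unknown row for leavers whose use was not assessed to the end of their participation.

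The cost is a few sentences and a slightly longer exit assessment, with no added visit. The change to 8.3 helps only leavers who attend an exit assessment.
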